Clinical evaluation of the effect of the scanning pattern on complete-arch
implant scans (strategies IOS)

C.I. 22/645-E

November, 23th, 2022

Study protocol and Statistical Analysis Plan

November, 23th, 2022

INTRODUCTION AND BACKGROUND

Record-taking is a fundamental process and the starting point for manufacturing a dental prosthesis. The appearance of intraoral scanners (IntraOral Scanners (IOS)) has meant a revolution in this regard due to the advantages they provide, including better communication with both the patient and the dental laboratory, better comfort and acceptance by the patient, the immediacy in sending the file and saving space in the storage of digital models versus conventional ones. However, they are not exempt from problems, including their high cost, the learning curve, and difficulty achieving a reliable record in certain circumstances, including edentulous full-arch records.

Recordings of the edentulous full arch with IOSs pose a challenge due to the type of operation of these devices, which gradually collect and overlap information from small areas until completing a full arch. For this reason, different techniques have been proposed to improve the accuracy of this type of recording. In addition, if there is a case in which accuracy is crucial, it is complete edentulous arches with implants since, if the registration is not exact, the prosthesis manufactured on it will not have a passive fit in the mouth, which would lead to the appearance of both biological and mechanical complications.

Different studies have tried to analyze how various factors influence this accuracy, and these factors can be divided into factors related to the operator, the scanner, environmental conditions, or intraoral conditions—also different scanning strategies or heights and positions of the scan bodies. However, most of these works have been developed in an in

vitro environment. This fact is motivated by the greater ease of making the records and, as a more relevant fact, the possibility of obtaining a reliable reference model, employing a coordinate machine (Coordinate Measurement Machine (CMM)) or a desktop scanner, something that in an in vivo study it is not possible.

The present study aims to clinically analyze the accuracy of different intraoral scanning strategies and types of scan bodies in edentulous full arch registrations on implants.

JUSTIFICATION

Due to the importance of the accuracy in taking digital impressions in full-arch patients for the fabrication of restorations on implants, it is considered justified to study the influence of different scanning strategies and scan bodies on the accuracy of full-arch recording.

VIABILITY

The project could be considered viable by having all the instruments and apparatus necessary to develop the material and methods. It is estimated that the proposed methodology could be developed within the period described.

AIM

The purpose of this in vivo study will be to measure the influence of different scanning strategies (zigzag with conventional scan body, circumferential with conventional scan body, surface blocking with conventional scan body, zigzag with low profile scan body, standard strategy with low profile scan body) on the accuracy of the records obtained for a case of fixed rehabilitation on full-arch dental implants.

HYPOTHESIS

The null hypothesis will be that there are no significant differences in scanning accuracy (trueness and precision) between the different groups of digital impressions compared to the reference model (conventional impression with rigid splinting).

The alternative hypothesis will be that there are significant differences in scanning accuracy (trueness and precision) between the different groups of digital impressions compared to the reference model (conventional impression with rigid splinting).

MATERIAL AND METHOD

A patient will be selected who is susceptible to rehabilitation with a fixed prosthesis on implants, in good general health (ASA I and ASA II), without joint problems or limitation of opening, and who, after reading the information sheet, the patient and informed consent, and clarified any doubts, voluntarily agree to participate in the study.

A reference model will be taken with a high-precision conventional methodology such as Rigid Impression Splinting. A first impression will be taken with double-mix addition silicone (putty and fluid) with an open tray. From this record, a first model will be generated that will be used to splint the impression transfers with a rigid, low-shrinkage light-curing material, which will later be sectioned with discs. Subsequently, the transfers will be screwed with the splint in the mouth and rejoined using a low-shrinkage light-curing material, thus minimizing the possibility of accumulation of errors. A second impression will be taken dragging the entire set, and it will be cast in improved type IV plaster (GC Fujirock; GC), thus obtaining the master model. This model will be digitized using a laboratory scanner to get the reference digital model, against which the specimens resulting from the experimental groups will be compared.

Six experimental groups will be created based on the strategy-scan body used (1.- zigzag with conventional scan body (ZZ-SBL), 2.- circumferential with conventional scan body (C-SBL), 3.- surface blocking with scan conventional body (B-SBL), 4.- zigzag with low profile scan body (ZZ-SBL), 5.- a standard strategy with low profile scan body (STD-SBL), 6.- single pass with low profile scan body (OP-SBL) These experimental groups

will be scanned directly in the patient's mouth, to be compared with the reference model, called the "master model".

Based on previous studies, a sample size of n=15 is estimated for each group. A pilot study will be carried out with n=5, from which a statistical test (G* Power; University of Düsseldorf) will be carried out to calculate the sample size. All digitization procedures will be performed under lighting conditions of 1000 lux measured with a lux meter (LX1330B Light Meter; [name] Illuminance) and at a constant temperature of 24 +/- 2 °C. Once the files are obtained, they will be exported with the reference format for a 3-dimensional.STL (standard tessellation language) file to a metrology program (Geomagic Control X). The results will be compared with a reference file, and the deviations of the implant positions will be obtained using the best-fit algorithm. The mean square error (Root Mean Square) will be calculated.

statistical plan

Statistical tests will be developed to check the normal distribution of the samples, Shapiro-Wilk or Kolmogorov-Smirnov type. A priori tests will be carried out to verify the existence of statistically significant differences, and a posteriori for analyzing which groups such differences appear and their magnitude. Statistical power will be 95%, so those with p<.05 will be considered statistically significant differences. All statistical analysis will be performed using a statistical software program (IBM SPSS Statistics for Windows, v26; IBM Corp).

VARIABLES COLLECTED AND DESCRIPTION OF THE ACTIONS TO BE CARRIED OUT AND FINAL DESTINATION OF THE SAMPLES

The collected variable is the discrepancy in the position of the implants between the control model, reference, and the experimental groups, quantified as a Root Mean Square.

The samples, in this case, files, will be saved anonymously on a hard drive, named so that

the group to which they belong and the number of samples can be interpreted (Example: ZZ-SBL1). The scanning time and the number of frames will also be collected.

SCHEDEULE

December 2022-March 2023: collection, sample preparation, development of experimental methodology, and data collection.

April 2023-July 2023: Statistical analysis and writing of the manuscript.

ETHICAL IMPLICATIONS

To the best of the research team's knowledge, the most significant ethical implication lies in carrying out several recordings of the same patient. In this regard, it should be noted that, in addition to meeting the inclusion requirements, the participant wishes to participate completely voluntarily and know that the participant will not obtain any compensation, financial or in any other way. On the other hand, we must bear in mind that intraoral record-taking procedures with intraoral scanners can be considered harmless and painless, which simply means that the patient must keep his mouth open during the procedure.

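### All scans come from one mouth, yet the plan sets no scan order, session plan or operator, so drift or a session shift could pass for a difference between groups

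*Combined protocol and SAP*

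**What the plan says.** MATERIAL AND METHOD enrols one person: "A patient will be selected who is susceptible to rehabilitation with a fixed prosthesis on implants". It then says "Six experimental groups will be created based on the strategy-scan body used". Groups 1 to 3 use the conventional scan body (zigzag, circumferential, surface blocking). Groups 4 to 6 use the low profile body (zigzag, standard, single pass). The AIM stops at five groups, ending with "zigzag with low profile scan body, standard strategy with low profile scan body) on the accuracy of the records obtained". The sixth, "single pass with low profile scan body (OP-SBL", appears only in the method section.

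On numbers: "Based on previous studies, a sample size of n=15 is estimated for each group". This is to be recalculated after a pilot with n=5.

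On scanning conditions: "All digitization procedures will be performed under lighting conditions of 1000 lux measured with a lux meter", with temperature held at 24 +/- 2 °C. No section states the order of scans, the number of sessions, who scans, or when scan bodies are removed and refitted.

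The section on variables collected plans the RMS discrepancy, scanning time, number of frames, and file names made of a group code and a sample number. The schedule allows December 2022 to March 2023 for preparation and data collection together.

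The introduction says of what influences accuracy that "these factors can be divided into factors related to the operator, the scanner, environmental conditions, or intraoral conditions". Separately, it lists general problems of intraoral scanners, "including their high cost, the learning curve, and difficulty achieving a reliable record in certain circumstances".

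**The concern.** With a single mouth there is no allocation of patients. The order in which scans are taken is the only allocation in the study. The plan controls environmental conditions from its own list of influences but leaves the operator and intraoral conditions open.

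If a group is completed before the next begins, anything that changes over the scans moves with the groups: operator practice or fatigue, saliva, scanner calibration, refitting of scan bodies, a new session. The listed order also puts every conventional-body group before every low-profile group. A strategy could then look better or worse because of when it was scanned.

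The planned records would not clearly reveal this. The sample number runs within a group. Scanning time, placed beside the frame count, most likely means duration, but it is not defined. Groups 1 and 4 share the code ZZ-SBL, so that code does not identify the scan body.

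**Working it through.** **Inputs from the documents.** One mouth; six groups (five in the AIM); n=15 per group, provisional; p<.05. No SD, effect size, drift, session effect or named test is given, so n=15 cannot be re-derived and everything below on size is an illustration.

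**Assumptions.** Scan-SD = 1; no true group difference; groups scanned in listed order; linear drift of total size D from first to last scan; one-way ANOVA.

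**1. Number of scans.** 6 x 15 = 90; with five groups, 5 x 15 = 75.

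**2. Bias from drift.** Scan k is shifted by D(k-1)/89. The first group occupies positions 1 to 15 (mean 8) and the last 76 to 90 (mean 83). The shift between them is (83-8)/89 x D = 75/89 x D = 0.84 D. With 75 scans it is 60/74 x D = 0.81 D.

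**3. False positives.** The group means sit at ±0.5, ±1.5 and ±2.5 steps of 15D/89 around the overall mean. The sum of squared steps is 2 x (0.25 + 2.25 + 6.25) = 17.5. The noncentrality of the F test (5 and 84 df) is therefore about 15 x (15/89)² x 17.5 x D² = 7.46 D². Simulation gives:

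| Total drift D (scan-SD) | 90 scans, listed order | 75 scans, listed order |
|---|---|---|
| 0.25 | 7% | 7% |
| 0.5 | 14% | 13% |
| 1 | 49% | 45% |
| 1.5 | 88% | 83% |

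With no drift but one session per group, an assumed between-session SD of 0.25, 0.5 or 1 gives about 31%, 79% or 98%.

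**4. Adjusting afterwards.** Unadjusted, the SE of first versus last group is √(2/15) = 0.37. With run order as a covariate it is √(2/15 + Δ²/S), where Δ is the distance between the two groups' mean positions and S is the within-group sum of squares of position. Each group of 15 consecutive positions contributes 15 x (15² - 1)/12 = 280.
- 90 scans: S = 6 x 280 = 1680 and Δ = 75, so SE = √(0.133 + 5625/1680) = √3.48 = 1.87.
- 75 scans: S = 5 x 280 = 1400 and Δ = 60, so SE = √(0.133 + 3600/1400) = √2.70 = 1.64.

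Adjustment also needs a run order that the plan does not clearly keep.

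**5. Randomised rounds.** If each round contains every group once in random order and round is in the model, false positives stay at about 5% for D from 0 to 1.5, taking refitting variation as zero. Where refitting varies, comparisons across scan-body types need it in their error. For group 1 versus group 4, taken as a difference within each round with both types freshly seated and a re-seating SD of s, the SE is √((2 + 2s²)/15) on 14 df. For s = 0, 0.5 and 1 this is 0.37, 0.41 and 0.52. Power for a 1 SD difference, before any multiplicity adjustment, is then about 72%, 62% and 44%.

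**The case against.** The strongest objection is that the size is hypothetical. The documents do not say that groups run one after another, and they give no figure for drift, session shift or refitting variation. That stands. A reader might infer that the plan prescribes sequential scanning or that its results are biased; the text supports neither. It supports only that nothing prevents this. At a drift of 0.25 SD the inflation is small.

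A reader might also infer that no trace of order is kept. That is too strong. The sample number may show order within a group, and if scanning time meant clock time it would give some order across groups.

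It is tempting to pool groups 1-3 against groups 4-6 and call the result the scan-body effect. The design does not support this, whatever the order, because only zigzag is used with both bodies. In randomised rounds with no scan-body effect and no re-seating variation, a pooled test rejects in about 31% of trials if one unshared strategy is 1 SD worse, and in 84% if both on one side are. Nor does the plan propose such a test: its hypothesis concerns differences between groups. The interpretable scan-body comparison is group 1 versus group 4.

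Finally, changing scan bodies in every round is a real burden for one patient. A lighter scheme is acceptable, but strict alternation of the types is not enough. With five blocks of nine scans per type, the same type always comes first, which leaves a bias of 9/89 x D = 0.10 D. The type contrast then rejects in about 7% of trials at D = 1 and 9% at D = 1.5.

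**Conclusion.** The concern holds. The plan leaves the sequence, sessions and operator of all scans open and keeps no clear cross-group record, so it permits group to be confounded with time or session. Under the assumptions above, false positives run from about 7% to 88% for drifts of 0.25 to 1.5 scan-SD, against about 5% with randomised rounds. Later adjustment is a poor rescue, since the standard error for the extreme groups is about five times as large (1.87/0.37).

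The omission and the arithmetic of the design are certain; the drift actually present is unknown. The introduction names operator and intraoral conditions as influences on accuracy. The learning curve is mentioned there only as a general difficulty with scanners, so it should not be cited as evidence of drift in this study. The order should be settled before the first scan, because it cannot be repaired afterwards.

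**What to change.** 1. **Operator and records.** Use one operator for all scans, or balance operators over groups. Log a running number across all groups, the date, the session and the operator for every file. Define scanning time. Give groups 1 and 4 different codes.
2. **Randomised rounds.** Scan in rounds (15 if n=15 is kept), each containing every group once and completed within one session. Put the two scan-body types in computer-generated random order, and the strategies in random order within each type. Include round in the analysis. The scheme also works with five groups.
3. **If changing scan bodies every round is impractical.** Randomise strategies in rounds within each type, and run the types in several pairs of blocks with the order randomised within each pair. If each type is run only once, state that all comparisons across scan-body types are confounded with order, session and seating.
4. **Scan-body comparison.** Do not present a pooled test of type as a scan-body effect. Use group 1 versus group 4, with re-seating variation counted in its error.

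**Cost.** No extra patients or scans. Item 1 and randomisation within type need a random list and a few recorded fields. Full rounds need 30 seatings of the scan bodies (2 types x 15 rounds), against 10 with five blocks per type and 2 if each type is run once. That means more chair time, with the patient's mouth open longer or more visits.

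### Does leaving the post hoc test and its adjustment unnamed undermine the planned p<.05 and 95% power?

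*Combined protocol and SAP*

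**What the plan says.** The section on the statistical plan sets out two steps: an overall test for any difference, then tests "and a posteriori for analyzing which groups such differences appear and their magnitude". Neither test is named. The one line on error rates is "Statistical power will be 95%, so those with p<.05 will be considered statistically significant differences". The only assumption check mentioned is to "check the normal distribution of the samples, Shapiro-Wilk or Kolmogorov-Smirnov type".

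MATERIAL AND METHOD says "Six experimental groups will be created based on the strategy-scan body used". The AIM lists five strategies; the single-pass group is absent there. On size, MATERIAL AND METHOD says "Based on previous studies, a sample size of n=15 is estimated for each group. A pilot study will be carried out with n=5", and that a G*Power analysis of the pilot "will be carried out to calculate the sample size". The test, alpha, power and effect to be entered are not given.

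HYPOTHESIS states the null as "no significant differences in scanning accuracy (trueness and precision) between the different groups of digital impressions". ETHICAL IMPLICATIONS says "the most significant ethical implication lies in carrying out several recordings of the same patient".

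**The concern.** With six groups, locating the differences means up to 15 comparisons, yet the plan gives one threshold and one power figure without saying what either refers to. Normally the choice of post hoc test can wait until the analysis. Here n is still to be calculated, and the n required depends on the criterion applied to the pairs. If n were set for one pair at .05 and the pairs were later adjusted, power would fall well below 95%. If the pairs were left unadjusted, some equal strategies could be reported as different. Extra scans would all come from one patient, and the plan itself names repeated recording as its main ethical issue.

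Two smaller points add to the impression of looseness. The null hypothesis covers precision, so spread may differ between groups, but only normality is to be checked. The two zigzag groups also share an abbreviation.

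**Working it through.** **Inputs from the document.** Six groups (five in the AIM), provisional n=15 per group, threshold .05, and 95% described as power.

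**Assumptions.** Two-sided tests, independent normal scans, equal variance, one outcome (RMS). Differences are in SD units because the document gives neither an expected difference nor an SD.

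**1. The plan's own figure.** n=15 is attributed to previous studies. Without an effect size, SD or test it cannot be reproduced. What follows shows only what n=15 would imply under different readings.

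**2. Number of pairs.** 6×5/2 = 15 for six groups; 5×4/2 = 10 for five.

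**3. Critical values at n=15.** The standard error of a difference is √(2/15) = 0.365 SD, with 6×14 = 84 residual df.

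| Criterion | Critical t | Smallest significant observed difference |
|---|---|---|
| One pair at .05 (84 df) | 1.989 | 0.73 SD |
| Tukey, six groups (84 df) | 2.917 | 1.06 SD |
| Games-Howell, six groups (28 df at equal variance) | 3.056 | 1.12 SD |

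**4. Reading A: n sized on one unadjusted pair.** Power is P(t > critical value), with t noncentral and noncentrality d√(n/2). Setting this to 0.95 at n=15 gives d = 1.332 SD (noncentrality 1.332×√7.5 = 3.65). At that difference power is 0.950 unadjusted, 0.765 with Tukey and 0.717 with Games-Howell. Restoring 95% takes 24 or 25 scans per group, that is 6×24 = 144 or 6×25 = 150 scans instead of 6×15 = 90. If the power target were 80% (d = 1.035 SD), power would fall to 0.471 or 0.429. With five groups, 95% falls to 0.800 or 0.763.

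**5. Reading B: n sized on the overall test.** For a one-way ANOVA with 5 and 84 df the noncentrality is 90f². Power of 95% needs f = 0.484 (90×0.484² = 21.1). Power for a truly different pair then depends on the layout of the means:

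| Layout with f = 0.484 | Pair difference | Tukey | Games-Howell |
|---|---|---|---|
| Three against three | 0.97 SD | 0.402 | 0.365 |
| One against five | 1.30 SD | 0.738 | 0.689 |
| Two extremes, rest midway (extreme pair) | 1.68 SD | 0.950 | 0.927 |

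The overall test keeps its 95% in every row.

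**6. Pairs left unadjusted.** With all groups equal, the chance of at least one false positive is 0.358 if the pairs are tested regardless of the overall test, and 0.050 if they are tested only after it is significant. Gated in this way, with some groups truly different, it is 0.14 (three equal pairs) to 0.28 (one against five, the worst layout run).

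Gating also costs power. For a 1.332 SD pair, simulation (100,000 data sets) gives about 0.93 with one group against five and 0.79 with two extremes and the rest midway, against 0.95 ungated. So leaving pairs unadjusted does not simply preserve the power once the overall test comes first.

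**The case for a change.** The strongest case for a change is timing. The text ties neither .05 nor 95% to anything, n is still open, and locating the differences is the plan's stated second step. A sentence written before the pilot calculation would cost little, and under Reading A the fall in power is similar whatever n the pilot yields. Nor does the overall test protect unadjusted pairs once some strategies really differ.

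Much of this stands. The detail is absent, and unadjusted pairs would carry a 14–28% false-positive risk in the layouts run with true differences. But the plan does not call for unadjusted pairs, and using an adjusted post hoc test is the sensible choice at analysis. The 72–77% figure needs n sized on one unadjusted pair and adjustment added afterwards. Since the plan puts an overall test first and states its null across the groups, sizing on the overall test is at least as natural. The 95% is joined to p<.05 in a way that suggests a confidence level, in which case no power was promised for any pair.

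The remedy is not free either. Sizing on adjusted pairs means accepting a larger detectable difference (1.76 instead of 1.33 SD with Games-Howell at 95% power) or about 150−90 = 60 more scans of one patient. A rule that switches between Games-Howell and Dunn tests according to a normality check would bring its own difficulty: Dunn tests compare ranks, so with skewed data and unequal spread they do not compare means.

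**Conclusion.** The observation is correct, but no change to the plan follows. The post hoc test, its adjustment and the sizing criterion are unwritten details. An overall test at .05 followed by a standard adjusted post hoc test fits the two-step plan and gives sound conclusions, and an analyst who sees unequal spread can choose a procedure that allows for it. The repeated zigzag abbreviation is a clerical slip, since the full group names differ.

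The size depends wholly on the reading. Power for a truly different pair at n=15 is 72–77% if n was set on one unadjusted pair and the pairs are then adjusted, and about 36–95% if n was set on the overall test, whose own 95% is unaffected. These figures assume independent normal scans with equal variance, six groups with all pairs compared, and 95% meaning power. None is the trial's actual power, which the document does not allow anyone to compute. Whether to spend more scans of one patient on pairwise power is a fair trade-off for the investigators. The conclusion would weaken only if pairs were reported unadjusted, which the plan does not say.

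### The only file-naming rule shows the group, and no masking of the alignment and RMS step is described

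*Combined protocol and SAP*

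**What the plan says.** Three parts of the combined protocol and SAP bear on this.

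- **File names.** The section on variables collected and final destination of the samples describes the stored files as anonymous, and requires names from which "the group to which they belong and the number of samples can be interpreted (Example: ZZ-SBL1"). No other naming rule or file identifier appears in the plan.
- **Measurement.** Material and Method states: "Once the files are obtained, they will be exported with the reference format for a 3-dimensional.STL (standard tessellation language) file to a metrology program". There, "the deviations of the implant positions will be obtained using the best-fit algorithm", and the result is summarised as a root mean square (RMS).
- **Outcome.** The variables section states: "The collected variable is the discrepancy in the position of the implants between the control model, reference, and the experimental groups", expressed as RMS. Scanning time and number of frames are also recorded, but RMS is the only accuracy variable named, and the hypotheses concern accuracy alone.

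The plan is silent on who performs the alignment, whether that person also scans, the order in which files are processed, which surfaces enter the fit, whether any file may be excluded, and whether anyone is blinded.

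**The concern.** The comparison between strategies rests on a number that someone produces in metrology software after the scan is finished. At that stage masking is feasible even though the scanning operator must know the strategy. The plan does not use this opportunity, and its one rule on file names works against it.

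If the person running the software has any discretion, knowledge of the group could influence how it is used. A resulting shift in RMS would be fully confounded with strategy. The normality checks and group tests in the statistical plan could not separate it from a real difference in accuracy.

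**Working it through.** **1. What the text establishes**

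| Question | What the plan says |
|---|---|
| Can the group be read from the file name? | Yes, by rule |
| Is group masking described anywhere? | No |
| When are files named, relative to alignment? | Not stated |
| Who aligns the files? | Not stated |
| How much manual choice does the best fit allow? | Not stated |
| Are files processed in random order? | Not stated |

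One qualification applies to the first row. Material and Method gives the same code to two groups: group 1, "zigzag with conventional scan body (ZZ-SBL"), and group 4, zigzag with the low-profile scan body. The example name therefore shows the strategy but not which of these two groups the file belongs to. The other four codes each identify one group.

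**2. How far coded names can mask**

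The plan says: "Six experimental groups will be created based on the strategy-scan body used". Groups 1 to 3 use conventional scan bodies and groups 4 to 6 low-profile ones. The shape of the scan body would presumably be visible in the mesh (assumption).

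- All pairwise contrasts: 6 × 5 / 2 = 15.
- Contrasts across scan-body types: 3 × 3 = 9. Coding leaves these distinguishable.
- Contrasts within a scan-body type: 3 + 3 = 6. Coding can mask these.
- If surface blocking (group 3) can also be recognised in the mesh (assumption), groups 1 and 2 leave 1 contrast and groups 4 to 6 leave 3, so 1 + 3 = 4.

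**3. What a handling shift would do, if there were one**

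The plan gives no size for such a shift, so there is no figure of its own to reproduce here. The only input taken from it is n = 15 per group (Material and Method), which is itself provisional because a pilot is to be used to calculate the sample size. Assumptions: a two-sided two-group t-test at 5%, independent scans, no true difference, and a shift of b SD in one group caused by handling.

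- Degrees of freedom: 15 + 15 − 2 = 28. Critical value: 2.048.
- Noncentrality: b × √(15/2) = b × 2.739.
- Rejection probability: P(|T| > 2.048), with T noncentral t on 28 df.

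| Assumed shift b | Noncentrality | False-positive rate |
|---|---|---|
| 0 | 0 | 5.0% |
| 0.10 SD | 0.274 | 5.8% |
| 0.25 SD | 0.685 | 10.1% |
| 0.50 SD | 1.369 | 26.2% |

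For a one-way ANOVA of all six groups with one group shifted, the noncentrality is 15 × b² × 5/6 on 5 and 84 df. That is 0.781 at 0.25 SD and 3.125 at 0.50 SD, giving rejection rates of 8.5% and 21.8%.

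**The case against.** The strongest reply is that the naming sentence is a storage rule. It describes files on a hard drive, in a section whose title ends with the final destination of the samples, and it fixes no order relative to alignment. The measurement is attributed to an algorithm, and trimming, rejection and repetition of scans are not mentioned anywhere. On that view the real gap is an unspecified alignment procedure, and coded names would leave most contrasts unmasked anyway.

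Much of this stands, and it rules out several stronger readings:

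- **That files are named before metrology and the aligner knows the group.** A reader might infer this, but the documents give neither the sequence nor the person. They support only that nothing prevents it.
- **That manual choices do move the RMS.** The plan describes no such choices. It also does not say that alignment is automated, so the question is open in both directions.
- **That calling the files anonymous contradicts naming them by group.** The word reads naturally as protecting the patient's identity. The plan makes no claim of group masking.
- **That the false-positive rate will be 10% or 26%.** Those rates follow from assumed shifts and independent scans. The plan takes repeated scans of one patient and names no specific test for comparing groups, and at 0.10 SD the effect is slight.
- **That coding blinds the measurement.** It does so for a minority of contrasts. Nor can it affect the scanning itself, where the operator must know the strategy.

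The reply does not dispose of the point. The plan goes beyond silence on masking by setting a rule that displays the group. The within-scan-body contrasts that coding can protect are comparisons of strategy, which is what the study sets out to compare.

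**Conclusion.** The concern holds in a limited form. The only naming rule makes the group readable (for the shared zigzag code, the strategy), no masking of the alignment and RMS step is described, and so a plan followed as written leaves the route for assessor bias open. This is a weakness in design, and the documents contain no evidence that bias would occur. Its size cannot be derived from them. It may be negligible if alignment is fully automated, and the percentages above only illustrate why even a modest differential shift would matter at 15 scans per group. The change is worth making because it is specific and cheap, and because no later analysis can remove the problem. It should be made but is not critical.

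**What to change.** Before alignment begins:

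1. At export, use a script to give each STL file a unique random code. Store the key (group and repeat number) apart from the person who aligns.
2. State who performs the alignment. Write one fixed alignment procedure, including which surfaces enter the fit and any grounds for exclusion, and apply it identically to every file.
3. Process the files in random order, and decide any exclusion on coded files.
4. Lock the RMS table, then merge the key.
5. State the limit of the remedy: scan-body type, and possibly surface blocking, would presumably remain recognisable. Coding then protects at most 6 of the 15 pairwise contrasts (4 if blocking is recognisable), while the fixed procedure covers all 15.
6. Give groups 1 and 4 distinct labels so that the key is unambiguous.

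The cost is a small script, a key file and a short written procedure for about 90 files (6 × 15, if the provisional sample size is kept). No extra scans or staff are needed, provided someone already on the team other than the aligner can hold the key.
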